## 5.7 SF36

The SF-36 consists of eight scaled scores (vitality, physical functioning, bodily pain, general health perceptions, physical role functioning, emotional role functioning, social functioning and mental health), which are the weighted sums of the questions in their section. Each scale is directly transformed into a 0-100 scale and a higher score represents a better health for that domain. Standardised physical and mental health scores are then calculated which for a general UK population are expected to be approximately normally distributed with mean 50 and standard deviation 10. [20]

The SF-36 questionnaire will be administered at baseline, 6 months, 12 months and 24 months. Then the scores for the summary measures of SF36, (Physical score and mental health score) will be given at each timepoint.

SF-36 component summary scores will be analysed using a linear regression model, adjusting for time point, treatment group, time by treatment group interaction, baseline SF-36 scores (all modelled as fixed effects) and allowing random intercepts for patients.

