## 1.5 Randomisation

Patients who fulfil the eligibility and have given written informed consent and have sufficient time for discussion and consideration, are randomised (in a 1:1 ratio) to one of two groups to receive either their routine cardiac surgery with no additional procedure or their routine cardiac surgery with an adjunct maze procedure.

Patient allocations are computer generated by the trial statistician and are in random permuted blocks of variable lengths, stratified by surgeon and by planned cardiac procedure (CABG, aortic valve, mitral valve, combined procedure).

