### 3.2 Quality of life populations

A separate quality of life population will be formed for the analysis of each questionnaire (SF36). Each population will comprise all patients who return an analysable baseline questionnaire, regardless of subsequent questionnaire return: patients without analysable baseline questionnaires will be excluded from the analysis, regardless of subsequent questionnaire return.

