### 4.2 Baseline data collection

We adhere to the ACC/AHA/ECS 2006 Guidelines which recommend that the initial patient description includes demographics, type and duration of AF and the planned cardiac procedure.

The first 4-day ECG recording starts after the patient attends the preadmission clinic and has consented to participate. All other baseline measurements are recorded on the day of admission for surgery. Once these measurements have been taken, the patient is registered with the co-ordinating centre's R&D unit and randomised as described in Section 1.5.

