## Return to SR

The intermediate primary outcome, whether patient returns to SR at 12 months, will be summarized according to the group to which they were randomised. The comparison between the heart rhythm (AF or SR) at the baseline and 12 months will be also summarized.

For the primary endpoint analysis, the rate in SR for Routine treatment group will be compared to that for Routine+Maze treatment group using a binary logistic regression model, which will include surgeon (as a random effect), surgical procedure and baseline heart rhythm as fixed effects. The odds ratio for the rate of return to SR at 12 months of Routine treatment group against Routine+Maze treatment group will be reported with 95% confidence interval and p-value for the data seen, under the null hypothesis that the rates of return to SR at 12 months are no different between the pairs of groups.

The adequacy of the logistic regression models for the primary endpoint will be assessed by examining the following statistics and relevant graphical summaries:

Pearson Residuals/Deviance (Half-normal plots)

Leverage values.

Cook's Distance.

Cross validation probabilities (the probability of a particular observation, conditional on the remaining observations).

L-statistics (the influence of an observation on the difference in deviance due to fitting an the treatment effect).

Actual percentage time in AF across the 4 days of monitoring at baseline and at 12 months, i.e. the percentage of time that the patient is in AF if their predominant rhythm is SR, is reported by treatment group. Based on the interim report, the percentage time

in AF is almost dichotomized at 0% and 100%. Therefore, only summary statistics are reported in this case.

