## 5.6 Key Secondary Endpoint Analysis

The key secondary endpoint, the rate to return stable SR at 24 months will be analysed in a similar way to the rate of return to SR at 12 month, but will include only those patients for whose measurements are available. The rate in SR at 24 months for Routine treatment group will be compared to that for Routine+Maze treatment group using a binary logistic regression model including baseline heart rhythm, surgeon, surgical procedure and treatment group. The odds ratio for the rate of return to SR at 24 months of Routine treatment group relative to the Routine+Maze group will be reported with 95% confidence interval and p-value for the data seen, under the null hypothesis that the rates of return to SR at 24 months are no different between the pairs of groups.

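### The SF-36 model omits the two randomisation factors, so its standard error is overstated if they predict SF-36 beyond baseline; separately, section 3.2 discards follow-up scores of patients without a baseline form

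*SAP*

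**What the plan says.** - **Allocation.** Section 1.5 uses permuted blocks "stratified by surgeon and by planned cardiac procedure", the procedure having four categories.
- **SF-36 model.** Section 5.7 analyses the component summary scores by linear regression on time point, treatment group, "time by treatment group interaction, baseline SF-36 scores (all modelled as fixed effects) and allowing random intercepts for patients". It has no surgeon or procedure term. Section 5.2 says that the variables specified for a model are the ones fitted, so the omission would carry through to the analysis.
- **Sinus rhythm models.** At 12 months (section 5.4, Return to SR) the logistic model is one "which will include surgeon (as a random effect), surgical procedure and baseline heart rhythm as fixed effects". At 24 months (section 5.6) it is a "binary logistic regression model including baseline heart rhythm, surgeon, surgical procedure and treatment group".
- **SF-36 population.** Section 3.2 states that "patients without analysable baseline questionnaires will be excluded from the analysis, regardless of subsequent questionnaire return".
- **Timing.** Section 4.2 places baseline measurement before allocation: "Once these measurements have been taken, the patient is registered with the co-ordinating centre's R&D unit and randomised".

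**The concern.** Two separate matters bear on the precision of the SF-36 comparison.

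**Strata.** Stratified allocation balances the arms on surgeon and procedure. If those factors are prognostic, the balance lowers the true sampling variance of the treatment effect. A model without them leaves their contribution in its error terms (here mainly the patient intercept) and reports a standard error that ignores the benefit. The estimate itself is unharmed, but the reported interval is too wide.

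**Exclusion.** A randomised patient with usable scores at 6, 12 and 24 months is removed because one pre-randomisation form is missing. The resulting standard error is correct for the patients kept, but larger than it would be with the discarded scores.

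At stake is some power and some interval width for a secondary quality-of-life outcome (section 2.2).

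**Working it through.** The SAP states no effect size, standard deviation, power or standard error for SF-36, so there is no figure to reproduce. Neither the variance share of the strata nor the share of missing baseline forms is given; both are assumptions below.

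**1. Strata omitted.** Let r be the share of baseline-adjusted variance explained by surgeon and procedure. With near-complete balance the true variance is proportional to 1 − r, while the model reports one proportional to 1. Reported over true standard error = 1/√(1 − r).

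| r (assumed) | 1/√(1 − r) | actual two-sided type I error at nominal 5% | power where a correct standard error gives 80% |
|---|---|---|---|
| 0% | 1.000 | 5.0% | 80% |
| 2% | 1/√0.98 = 1.010 | 4.8% | 79% |
| 5% | 1/√0.95 = 1.026 | 4.4% | 79% |
| 10% | 1/√0.90 = 1.054 | 3.9% | 77% |

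With f the second column, the third is 2Φ(−1.960f) and the fourth is Φ(1.960 + 0.842 − 1.960f).

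*Check by simulation:* 400 patients, permuted blocks within surgeon by procedure, 25 surgeons assumed, 2,000 runs per setting, nobody dropped. The mean reported standard error of the model without strata, divided by the observed spread of its estimates, was 0.995 at r = 0, 1.012 at 2%, 1.035 at 5% and 1.055 at 10%. The simulation error of each ratio is about 1/√(2 × 2,000) = 1.6%, so these agree with the formula, but the 2% result cannot be told from no effect. At r = 10% the estimates themselves varied almost equally without and with the strata (0.7535 against 0.7493). The fault is therefore in the reported error, not in the actual precision of the estimate. The reported standard error without strata was 1.040 times that with strata at r = 10%, 1.015 at 5%, 1.001 at 2% and 0.993 at 0%. The gain is slightly below the formula, as expected when 27 indicator terms are fitted.

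**2. Patients without a baseline form excluded.** Let m be the share without an analysable baseline.

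- Upper bound on the loss: 1/√(1 − m). At m = 5%, 1/√0.95 = 1.026; at m = 10%, 1/√0.90 = 1.054.
- This bound treats each restored patient as if the baseline score were known. If baseline and follow-up correlate at ρ, a patient without a baseline carries a fraction 1 − ρ² of the information. The avoidable inflation is √[((1 − m) + m(1 − ρ²))/(1 − m)].
- m = 5%, ρ = 0.6: √[(0.95 + 0.05 × 0.64)/0.95] = √(0.982/0.95) = 1.017.
- m = 5%, ρ = 0.7: √[(0.95 + 0.05 × 0.51)/0.95] = √(0.9755/0.95) = 1.013.
- These two figures assume that the restored patients are weighted by their information. If a mean fill with a missing indicator is fitted with one common residual variance, the factor is √{(1/0.95)/[0.95 + 0.05/(1 − ρ²)]}. At ρ = 0.6 this is √(1.0526/1.0281) = 1.012, and at ρ = 0.7 it is √(1.0526/1.0480) = 1.002.

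The two parts should not be multiplied into one figure: the first is a misreported error, the second a correct error from fewer patients.

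**The case against.** **The inflation may be nil.** A reader might infer from the missing terms that the SF-36 standard errors are too large. The SAP does not show this. The baseline score is already in the model, and surgeon and procedure matter only for what they add to it. This objection stands, and the point is therefore conditional.

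**Few baseline forms may be missing.** Baseline measures are taken before randomisation, so missing forms may be rare and the exclusion does not by itself favour an arm. This stands. A reader might read section 3.2 as a source of bias; the documents do not support that.

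**Sections 2.3 and 3.2 do not conflict.** A reader might contrast the imputation of missing covariates in 2.3 with the exclusion in 3.2. The rule in 2.3 is written for the primary analysis model and its covariates (baseline rhythm, surgeon, procedure) and does not reach SF-36. Sections 3.2 and 5.7 agree with each other: the model needs a baseline score and the population is defined by having one. The exclusion is a stated choice that costs data, not a contradiction.

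**SF-36 is not the only model without the strata.** The main QALY regression in 5.4 has no procedure term and includes surgeon only under conditions; the drug-use models in 5.8 have neither. This stands, so the sinus rhythm models show that the factors are available and usable, not that the SAP has a uniform rule which 5.7 breaks.

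**SF-36 has modest standing.** Section 2.2 lists it beside EuroQoL and NYHA without ranking, and it is not named in the secondary objectives. Calling it the main quality-of-life measure would go beyond the text.

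None of this removes the two facts: the randomisation factors are absent from the model, and collected follow-up scores are discarded.

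**Conclusion.** The point holds in a limited, conditional form.

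- **Strata:** if surgeon and procedure explain an assumed 2 to 10% of baseline-adjusted SF-36 variance, the reported standard error is about 1 to 5% too large. If they explain none, there is no inflation. The error is conservative.
- **Exclusion:** the standard error is valid, and at most 2.6% larger if an assumed 5% lack a baseline form. About 1.3 to 1.7% of that is recoverable at an assumed correlation of 0.6 to 0.7 with efficient weighting, and less with a simple mean fill.

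This is an optional improvement to a secondary endpoint, worth making because it is cheap. Neither bias nor inflated type I error follows from the SAP as written.

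**What to change.** 1. **Section 5.7:** add planned procedure, as used at randomisation, as a fixed effect, and surgeon as a random effect. Put surgeon under the condition that section 5.4 already sets for the QALY regression (feasible to fit, with a positive variance component), because the SF-36 model also has a patient random intercept.
2. **Section 3.2:** include every randomised patient with at least one post-baseline SF-36 score, subject to the consent exclusions in section 3.1. Fill a missing baseline score without regard to arm, either by the overall baseline mean with a missing indicator or by imputation from baseline covariates, and name the method. The mean fill is simplest but recovers the least if one residual variance is assumed.
3. Report by arm the number of patients whose baseline score was filled.

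The cost is two model terms and a sentence or two of text. No new data are needed: both factors are already held for randomisation.

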## 5.8 Additional Secondary Endpoint Analyses

To investigate whether the adjunct maze procedure decreases thromboembolic neurological complications (e.g. stroke), the patients who have suffered a stroke will be summarized within 12 months of surgery and the overall proportion of stroke events will be calculated by treatment group, using the total number of patients participating in the trial as the denominator. The absolute differences between the proportions for Routine treatment group and Routine+Maze group will be tested by Fisher's exact test, and reported along with 95% confidence intervals for differences in proportions.

The number of recruited patients who use anti-arrhythmic drugs will be tabulated by time points (at baseline, discharge, 6 weeks, 6 months, 12 months and 24 months) and drug categories (Sotalol, Amiodarone and Flecainade). Logistic Regression for the outcome of each patient (1=have one or more drugs during time period t, 0=have no drug during time period t) will be fitted, including drug category, time period using drug, baseline drug usage and treatment group as independent variables. The odds ratio for using anti-arrhythmic drug in the Routine treatment group relative to the Routine+Maze group will be reported with 95% confidence interval and p-value for the data seen, under the null hypothesis that the usage of anti-arrhythmic drugs is no different between the groups.

In the similar way, the number of recruited patients who use anti-coagulant drugs will be tabulated by time point (at baseline, discharge, 6 weeks, 6 months, 12 months and 24 months) and drug categories (Warfarin, Sintrome and other anticoagulants). The logistic regression for the outcome of each patient (1=have one or more drugs during time period t, 0=have no drug during time period t) will be fitted, including the drug category, time period using drug, baseline drug usage and treatment group. The odds ratio of using anti-coagulant drug in the Routine treatment group relative to the Routine+Maze group will be reported with 95% confidence interval and p-value for the data seen, under the null hypothesis that the usage of anticoagulants drug is no different between the pairs of groups.

The occurrence of atrial flutter and atrial tachycardia ("organised atrial arrhythmia" - OAA) and junctional rhythm (JR) will be summarised by arm. An exploratory analysis will look at the relation between the completeness of the lesion set and the occurrences of OAA and JR.

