### 2.2 Secondary outcomes

Clinical endpoints of SR at 24 months after surgery, overall survival and stroke-free survival, incidence of anticoagulant-related haemorrhage.

Health-related QoL measured by the EuroQoL, SF-36 and NYHA.

Resource use and cost-effectiveness of the adjunct maze procedure.

Anticoagulant and antiarrhythmic drug usage.

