### 4.3 Data collection during and after surgery

Data collection is based on the recommendations of Shemin et al.[13] and includes procedural details-including the lesion set in the experimental group. Data collected after surgery includes: mortality, stroke/thromboembolic events, medications, EuroQoL, health-related quality of life, cardioversion plan if appropriate, 4-day ECG recordings, resource use, adverse events.

Data are collected during surgery, at discharge, 6 weeks after surgery (at a routine service visit), at 6, 12 and 24 months after surgery during out-patient research visits and annually thereafter by telephone follow-up.

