### 5.1 General calculations

All statistical analyses and reporting will comply with CONSORT guidelines where possible.

Confidence intervals for a single proportion shall be calculated using the Exact method. Confidence intervals for a difference between independent proportions shall be calculated using Exact intervals (Method 8 of [16]).

All percentages will be calculated using the total number of patients within the specified analysis population, percentages will be reported to 1 decimal place. All statistical tests will be 2-sided and performed at the 5% significance level. All analyses will be carried out using SAS.

For summary statistics, the number of non-missing items, the means, standard deviations, medians, upper and lower quartiles and minima and maxima will be summarised to one more decimal place than the data are collected.

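### Stroke is compared only to 12 months although follow-up and the final analysis run to 24 months, and stroke-free and overall survival are declared without an intention-to-treat analysis

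*SAP*

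**What the plan says.** - **Declared outcomes.** SAP section 2.2 lists among the secondary endpoints "overall survival and stroke-free survival, incidence of anticoagulant-related haemorrhage". Objective 2 in section 1.3.3 asks whether the maze procedure reduces thromboembolic neurological complications and sets no time limit.
- **Data collected.** Section 4.3 includes mortality and stroke in the post-operative data, with visits "at 6, 12 and 24 months after surgery during out-patient research visits" and yearly telephone contact afterwards. Section 5 expects the final analysis once every patient has reached 24 months.
- **Stroke analysis.** Section 5.8 says "the patients who have suffered a stroke will be summarized within 12 months of surgery". A proportion of stroke events is then to be calculated for each treatment group, and the divisor is described in these words: "using the total number of patients participating in the trial as the denominator". The difference between arms "will be tested by Fisher's exact test, and reported along with 95% confidence intervals for differences in proportions".
- **Deaths.** Section 5.9 lists deaths with the adverse events, grouped by the intervention received. Section 3.1 makes intention-to-treat the primary method.

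**The concern.** The stroke window is half as long as the follow-up, and the SAP gives no reason. The same section models anticoagulant and anti-arrhythmic use up to 24 months. The report would therefore show anticoagulant use in the second year with no stroke comparison for that year, although objective 3 asks whether anticoagulation can be withdrawn safely.

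In addition, a crude stroke proportion is not stroke-free survival. In the declared outcome death is an event. In the proportion, a patient who dies or is lost before any stroke stays in the denominator as a patient without stroke. Section 5 contains no time-to-event method, so anyone reporting the declared survival outcomes would have to choose one after the data are available.

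**Working it through.** **Step 1: does any other section fill the gap?** Taking the candidates in turn:
- Section 5.4 puts deaths into the QALY endpoint as zero utility. That is not an estimate of survival.
- Section 5.9 counts deaths by intervention received, not by randomised arm.
- Section 4.5 does not expect the ONS tracking data to form part of the primary analysis up to 24 months.
- The separate plan mentioned in section 5.9 covers health economics.

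None gives a method for stroke-free or overall survival by randomised arm. Anticoagulant-related haemorrhage has no dedicated analysis either.

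**Step 2: trial size.** The SAP gives no stroke rate, event count or stroke power, so there is no stroke figure to reproduce. Its sample size figures do reproduce. For 45% vs 30% at 80% power and two-sided 5%, the usual formula gives 163 per group, or 176 with continuity correction, as stated in section 1.4.1. For QALYs (200 per group, difference 0.083, SD 0.3) power is 79.0%, against the stated approximate 80%. I use 200 per arm below.

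**Step 3: share of strokes left out.** Let q be a perioperative stroke risk and h a constant annual hazard afterwards. Both are **assumptions**, and the model ignores deaths.

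p(t) = q + (1 − q)(1 − exp(−h·t)); share after month 12 = [p(2) − p(1)] / p(2), with t in years.

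Example with q = 2%, h = 1%: p(1) = 0.02 + 0.98 × 0.00995 = 0.0298; p(2) = 0.02 + 0.98 × 0.0198 = 0.0394; share = 24.5%.

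The last two columns give the exact power of Fisher's test with 200 per arm, taking p as the control risk and assuming a risk ratio of 0.5.

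| q | h per year | p at 12 months | p at 24 months | Share after month 12 | Power, 12 months | Power, 24 months |
|---|---|---|---|---|---|---|
| 0 | 2% | 1.98% | 3.92% | 49.5% | 4% | 13% |
| 0 | 4% | 3.92% | 7.69% | 49.0% | 13% | 30% |
| 1% | 2% | 2.96% | 4.88% | 39.4% | 9% | 17% |
| 1% | 1% | 1.99% | 2.96% | 32.9% | 4% | 9% |
| 2% | 2% | 3.94% | 5.84% | 32.6% | 13% | 22% |
| 2% | 1% | 2.98% | 3.94% | 24.5% | 9% | 13% |
| 3% | 1% | 3.97% | 4.92% | 19.4% | 13% | 17% |

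The share is about one half only when there is no perioperative excess. With q of 1% to 3% it is 19% to 39%. Power rises in every row but never exceeds 30%.

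**Step 4: the denominator.** Take 10 vs 4 strokes as an illustration.
- Over 200 per arm: 5.0% vs 2.0%, difference 3.0 points, Fisher p = 0.17.
- Over 400 for each arm: 2.5% vs 1.0%, difference 1.5 points, Fisher p = 0.18.

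A pooled denominator would halve the rates and the difference but leave the ratio at 2.5. Whether the SAP means this is taken up under the objection.

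**The case against.** **The 12-month limit may not govern the test.** The sentence in section 5.8 goes on to an overall proportion, which could mean a second quantity over all follow-up. That reading is possible but less natural: no other window is stated, and the proportion follows directly from the 12-month summary. If it was intended, the text still needs to say so.

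**The proportion is a legitimate measure.** With complete follow-up, patients with a stroke divided by all patients in the arm is the cumulative incidence of stroke with death as a competing event. It suits objective 2, which concerns stroke rather than stroke or death. This stands, and is a reason to keep the proportion. It does not supply the stroke-free survival declared in section 2.2.

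**The denominator.** A reader might infer that the arm rates would be wrong because both arms are divided by the whole trial. The SAP does not support that. The same sentence calculates by treatment group. Fisher's test and the section 5.1 interval for independent proportions both need each arm's own total. Section 5.1 also sets the general rule: "All percentages will be calculated using the total number of patients within the specified analysis population". The phrase most likely means that nobody is dropped for missing data. What remains is loose wording, which also moves between patients with a stroke and stroke events.

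**Little is gained statistically.** Power for stroke is low at either time point, and a Cox model stratified by surgeon would spread few events over many strata. Both points stand and shape the fix.

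**Conclusion.** The point holds. As most naturally read, section 5.8 keeps strokes in months 12 to 24 out of the planned test. Stroke-free and overall survival are declared without an intention-to-treat analysis.

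The size is uncertain because the SAP gives neither stroke rates nor timing. Under the assumed rates, roughly 19% to 50% of 24-month strokes fall after month 12, the share being smaller the larger the perioperative excess.

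Three stronger readings are not supported:
- **Half the events are discarded.** One half is the top of the range and needs a constant hazard with no perioperative excess. The events are still collected, and section 5.9 summarises adverse events.
- **Mortality is ignored altogether.** Deaths are listed in the safety analysis and enter the QALY endpoint. What is missing is an estimate of survival by randomised arm.
- **Effects of withdrawing anticoagulants fall mainly in the omitted year.** Nothing in the SAP says when they would appear.

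**What to change.** 1. Analyse stroke-free survival (first stroke or death) and overall survival to 24 months by randomised arm in the intention-to-treat population. Use Kaplan-Meier curves with a log-rank test or a simple Cox model, not stratified by surgeon because events will be few. State the time origin and the censoring rule.
2. Report the proportion of patients with at least one stroke at both 12 and 24 months, keeping Fisher's exact test and the confidence interval for the difference.
3. Reword the denominator as the number of intention-to-treat patients in each arm, and count patients rather than events.
4. Tabulate anticoagulant-related haemorrhage by arm over the same 24 months.

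The cost is some SAP wording and a few standard tables from data already collected. No added power should be claimed as the reason: the benefit is that the declared outcomes are estimated completely, by a method fixed in advance.

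### The drug-use logistic regressions in SAP section 5.8 give no valid treatment odds ratio on any reading of the data layout: either drug category separates the outcome, or correlated rows of one patient are analysed without a patient term

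*SAP*

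**What the plan says.** Section 5.8 of the SAP tabulates anti-arrhythmic use by "time points (at baseline, discharge, 6 weeks, 6 months, 12 months and 24 months" and by "drug categories (Sotalol, Amiodarone and Flecainade". It then specifies "Logistic Regression for the outcome of each patient (1=have one or more drugs during time period t, 0=have no drug during time period t", with the predictors "including drug category, time period using drug, baseline drug usage and treatment group as independent variables". The result to be reported is fixed: "The odds ratio for using anti-arrhythmic drug in the Routine treatment group relative to the Routine+Maze group will be reported with 95% confidence interval", with a p-value.

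The anticoagulant analysis follows the same pattern. Its categories are "drug categories (Warfarin, Sintrome and other anticoagulants" and its model is described as "including the drug category, time period using drug, baseline drug usage and treatment group".

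Three other places bear on the point:
- Section 5.7, directly before, fits SF-36 scores over time and provides for repeated measures by "allowing random intercepts for patients".
- Section 5.2 rules out model building: every variable named for a model goes into it.
- Section 5.1 sets all tests at two-sided 5%.

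**The concern.** Two features of the specification do not fit together. The outcome has one value per patient per period and period is a covariate, so each patient supplies several rows; yet nothing in the model links those rows. And the levels of drug category are all active drugs, while the outcome is use of any drug, so a row with outcome 0 has no level to take.

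Secondary objectives 3 and 4 (section 1.3.3) ask whether the maze procedure allows anticoagulants to be withdrawn, and antiarrhythmics to be reduced or withdrawn, safely. The two regressions are the SAP's only formal between-group comparisons of drug use. If the model cannot be fitted, the analyst must improvise after seeing the data. If it is fitted on stacked rows without a patient term, a chance difference in drug use is declared significant too often.

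**Working it through.** **Inputs.** From the SAP: 200 patients per group, 400 in total (section 1.4.1); six time points, five of them after baseline (5.8); three drug categories per model (5.8); two-sided 5% (5.1). The SAP gives no figure for the drug-use analyses, so there is none to reproduce, and it gives no within-patient correlation. Assumed here: a normal patient random intercept on the log-odds scale with SD 1, 2 or 4, which produces mean between-visit correlations of about 0.17, 0.39 and 0.63.

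**Step 1: which data layouts are possible?**

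| Layout | Drug category | Within-patient correlation |
|---|---|---|
| A. One row per patient and period, outcome any use (as written) | undefined when outcome = 0 | not modelled |
| B. One row per patient, period and drug | defined | not modelled; up to 5 × 3 = 15 rows per patient |
| C. A separate model for each period | undefined when outcome = 0 | not an issue, but the period covariate would be constant |

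The listed period covariate contradicts layout C. Reading that covariate as duration of use does not help, since duration also exists only for users.

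**Step 2: layout A.** There are two ways to handle the missing category.
- *Drop rows without a category.* Only rows with outcome 1 remain. In one simulated data set, 714 of 400 × 5 = 2000 rows remained, all with outcome 1. No odds ratio exists.
- *Add a level for no drug.* The outcome is then 0 exactly when category is none. The likelihood approaches its maximum as the category coefficients diverge, whatever the treatment coefficient, so treatment is not identified. In the same data set, simulated with a real treatment effect, the model with treatment alone gave a log odds ratio of −0.71 (SE 0.10). Adding category gave 0.00 (SE about 16,000), without convergence.

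Section 5.2 does not let the analyst drop category.

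**Step 3: cost of the missing patient term once category is removed from layout A.** Simulated with no treatment effect: 400 patients, 5 visits, ordinary logistic regression on treatment, baseline use and period, compared with the same fit using patient-clustered errors (about 1000 trials per setting).

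| Random-intercept SD (assumed) | Between-visit correlation | Type I error, ordinary | Type I error, clustered | Clustered SE ÷ ordinary SE |
|---|---|---|---|---|
| 1 | about 0.17 | about 11% | about 5% | about 1.26 |
| 2 | about 0.39 | 17–18% | about 5% | about 1.46 |
| 4 | about 0.63 | about 21% | about 5% | about 1.60 |

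The last column can be checked against the third. If the SE is too small by a factor k, the type I error is 2 × [1 − Φ(1.96/k)]. This gives 12.0% for k = 1.26, 17.9% for 1.46 and 22.1% for 1.60, which agrees within simulation error of about one percentage point.

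**Step 4: layout B.** Rows stacked by drug, with category, period, baseline use of that drug and treatment in the model, and a separate patient intercept for each drug (500 trials per setting, no treatment effect). Ordinary type I error was 10.4%, 16.8% and 21.0% for SDs of 1, 2 and 4; clustering on patient gave 4.6%, 5.0% and 4.8%.

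**The case against.** Several points on the other side deserve weight.

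- *The SAP does not say that visits are independent.* True. Section 5.8 is silent, and a programmer might add a patient effect unprompted. But section 5.7 writes the patient effect out for SF-36 and section 5.8 does not. An ordinary logistic regression is the natural reading, so this is an omission that needs filling.
- *The two faults do not occur together.* Also true. A reader might infer that the plan produces both a separated model and an over-precise p-value. Under layout A with category included, no usable p-value appears. Under layout B, category is a proper predictor and only the clustering fault remains, though B departs from the stated any-drug outcome. The supported statement is that the layout is ambiguous and neither version works.
- *The inflation could be put higher.* An unadjusted design effect, √(1 + 4ρ), gives SE factors of 1.30, 1.60 and 1.88 at ρ = 0.17, 0.39 and 0.63, and simulation without baseline use gives a type I error of about 13%, 22% and 29%. Those figures do not apply: section 5.8 includes baseline drug use, which absorbs part of the between-patient variation.
- *The objectives do not depend on these odds ratios alone.* This stands. Objectives 3 and 4 concern safe withdrawal or reduction, which also draws on stroke, anticoagulant-related haemorrhage and adverse events. The tables of users by time point and drug are unaffected.

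**Conclusion.** The concern holds for both drug-use models. As written, the treatment odds ratio either cannot be estimated (one row per patient and period, with category) or comes with an interval that is too narrow (rows stacked by drug). For a nominal 5% test the false-positive rate is roughly 10–21% over the assumed range, with standard errors too small by about 1.26 to 1.60 once category is removed. The size depends on the assumed correlation. The direction needs only that a patient's drug use is positively correlated across visits.

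A reader might infer that the trial's main conclusions are at risk. The document does not support that: these are additional secondary analyses, ranked below the key secondary endpoint of section 5.6, and neither primary endpoint nor the sample size is touched. The point should be fixed before analysis, but it is not critical to the trial.

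**What to change.** Rewrite both models in section 5.8 as follows:

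1. One row per patient per post-baseline visit (discharge, 6 weeks, 6, 12 and 24 months), with outcome any use of the drug class. Baseline use is a covariate only.
2. Predictors: treatment, visit and baseline use.
3. One pre-stated method for within-patient correlation. GEE clustered on patient with robust errors gives a population-averaged odds ratio; a patient random intercept gives a patient-specific one. The two differ in size, clearly so at high correlation, so the SAP should name one.
4. Remove drug category from the predictors and show it in the tables already planned.

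Further covariates, a treatment-by-visit term or visit-specific odds ratios are optional and not needed to repair the fault. The cost is a short SAP amendment and a few lines of SAS, with no new data. The downside is wider confidence intervals.
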